### **7.9.1 Analysis of Individual Plasma Concentrations and Pharmacokinetic Parameters for rosuvastatin, sildenafil and furosemide**

#### *Plasma Concentration*

Plasma concentration data for each victim drug (alone) and each victim drug in presence of edaravone will be listed by subject, treatment and nominal time point and summarised by treatment.

Individual and mean plasma concentration versus time curves will be plotted on both linear/linear and log/linear scales separately for rosuvastatin, sildenafil and furosemide. For individual plots actual time will be used. There will be two sets of individual plots: a) separate plots for each treatment (victim drug alone and victim drug + edaravone) with all subjects included and b) with separate plots for each subject with both treatments included.

#### *PK Parameters*

The following PK parameters for rosuvastatin, sildenafil, and furosemide will be calculated from measured plasma concentrations:  $AUC_{0-t}$ ,  $AUC_{0-24}$ ,  $AUC_{0-\infty}$ ,  $C_{\text{max}}$ ,  $t_{\text{max}}$ ,  $t_{1/2}$ ,  $\text{Kel}$ ,  $\text{MRT}$ ,  $\text{CL/F}$ ,  $V_z/F$ ,  $V_{ss}/F$

All PK parameters will be summarised by analyte alone and in combination with edaravone.

These parameters will also be listed. For all PK profiles for which the Kel has been calculated, the following will be listed:

- Number of data points used in the regression analysis for estimation of Kel.

- The lower and upper limits of the time period spanned by the data points used in the regression analysis for estimation of  $K_{el}$ .
- Adjusted R-squared value.
- Percentage of  $AUC_{0-\infty}$  extrapolated.

For  $C_{max}$ ,  $AUC_{0-t}$ ,  $AUC_{0-24}$  and  $AUC_{0-\infty}$  spaghetti plots will be produced showing individual changes from victim drug alone to victim drug + edaravone.

For  $C_{max}$ ,  $AUC_{0-t}$ ,  $AUC_{0-24}$  and  $AUC_{0-\infty}$  ratios (victim drug + edaravone / victim drug alone) will be calculated for each subject. These will be listed and summary statistics (N, n, mean, SD, median, minimum, maximum) for these will also be presented.

$C_{max}$ ,  $AUC_{0-t}$ ,  $AUC_{0-24}$  and  $AUC_{0-\infty}$  will be analysed as for the assessments of effect on pharmacokinetics of rosuvastatin, sildenafil, and furosemide by edaravone as explained in 7.9.3, but 90% CI for the ratio of  $AUC_{0-t}$  and  $AUC_{0-24}$  will not be used for the assessment of the effect of edaravone on rosuvastatin, sildenafil and furosemide.

### **7.9.2 Analysis of Individual Plasma Concentrations and Pharmacokinetic Parameters for Unchanged Edaravone, Sulfate Conjugate, and Glucuronide Conjugate (Cohort 1)**

#### *Plasma Concentration*

Plasma concentration data of unchanged edaravone, sulfate conjugate (group 2), and glucuronide conjugate (group 2) after administration of edaravone (alone) and in presence of each victim drug will be listed by subject, treatment and nominal time point.

Summary statistics (N, n, mean, SD, minimum, median, maximum, CV%, geometric mean and geometric CV%) will be calculated for plasma concentrations of each analyte at each time point by treatment. Plasma concentration data of unchanged edaravone after administration of edaravone alone will be summarized in each group and in combined groups.

Individual and mean plasma concentration versus time curves will be plotted on linear/linear scale for each analyte using actual and scheduled times respectively.

#### *Concentration at post-24 h*

Concentrations at post-24 hours of unchanged edaravone, sulfate conjugate (group 2) and glucuronide conjugate (group 2) are the pre-dose concentrations for each day during Day 6 to Day 13 (group 1) or Day 3 to Day 7 (group 2).

The ratio of concentrations at post-24 h on each day (Day 6 to Day 12 for group 1 or Day 3 to Day 6 for group 2) compared to the concentration at post-24 h on the last dosing day (Day 13 for group 1 and Day 7 for group 2) will be calculated using observed values (i.e., the data will not be log-transformed for calculation of the ratios). In the event that the pre-dose concentration is BLQ, the ratio will not be calculated for that day (in this case the result will be shown as not calculated [NC] in the listings and will be excluded from the summary statistics). The ratios on each day (Day 6 to Day 12 or Day 3 to Day 6) compared to the last dosing day will also be listed. The ratios each day (e.g., Day 7/Day 13) will be summarized using descriptive statistics.

#### *PK Parameters*

The following PK parameters for unchanged edaravone, sulfate conjugate (group 2) and glucuronide conjugate (group 2) will be calculated from measured plasma concentrations:  $AUC_{0-t}$ ,  $AUC_{0-24}$ ,  $AUC_{0-\infty}$ ,  $C_{max}$ ,  $t_{max}$ ,  $t_{1/2}$ ,  $Kel$ ,  $MRT^*$ ,  $CL/F^*$ ,  $V_z/F^*$ ,  $V_{ss}/F^*$  (\* only for unchanged edaravone)

The PK parameters will be listed. Summary statistics (N, n, mean, SD, median, minimum, maximum, geometric mean and geometric CV%) will be presented for all PK parameters by treatment (edaravone alone or in combination with each victim drug). The PK parameters of unchanged edaravone after administration of edaravone alone will be summarized in each group and in combined groups.

These parameters will also be listed. For all PK profiles for which the  $Kel$  has been calculated, the following will be listed:

- Number of data points used in the regression analysis for estimation of  $Kel$ .
- The lower and upper limits of the time period spanned by the data points used in the regression analysis for estimation of  $Kel$ .
- Adjusted R-squared value.
- Percentage of  $AUC_{0-\infty}$  extrapolated.

### 7.9.3 Assessments of effect on pharmacokinetics of rosuvastatin, sildenafil, and furosemide by edaravone

PK parameters  $AUC_{0-\infty}$  and  $C_{max}$  of rosuvastatin, sildenafil, and furosemide alone and in the presence of edaravone will be analysed for the assessments of effect on pharmacokinetics of rosuvastatin, sildenafil, and furosemide by edaravone.

#### *Descriptive Statistics:*

Pharmacokinetic parameters will be summarized by analyte (i.e. Rosuvastatin, Sildenafil and Furosemide) alone and in presence of edaravone.

#### *Statistical Analysis:*

A linear mixed effects model will be fitted to log-transformed PK parameters ( $AUC_{0-t}$ ,  $AUC_{0-24}$ ,  $AUC_{0-\infty}$ , and  $C_{max}$ ) including treatment as fixed effect and subject as random effect. Treatment will be victim drug + edaravone or victim drug alone. Estimates of mean difference between treatments will be obtained with 90% CI for the difference. These estimates and limits will then be back-transformed to obtain ratios of least squares geometric means A 90% CI for the ratio of  $AUC_{0-\infty}$  as well as  $C_{max}$  which lie entirely within the limits of 0.80 to 1.25 provides evidence of no effect of edaravone on rosuvastatin, sildenafil and furosemide.

### 7.9.4 Analysis of Individual Plasma Concentrations and Pharmacokinetic Parameters for Unchanged Edaravone, Sulfate Conjugate, and GlucuronideConjugate (Cohort 2)

#### *Plasma Concentration*

Plasma concentration data of unchanged edaravone, sulfate conjugate, and glucuronide conjugate after administration of edaravone in each meal condition and each race will be listed by subject, treatment and nominal time point.

Summary statistics (N, n, mean, SD, minimum, median, maximum, CV%, geometric mean and geometric CV%) will be calculated for plasma concentrations of each analyte at each time point by treatment.

Individual and mean plasma concentration versus time curves will be plotted on both linear/linear and log/linear scales separately for unchanged edaravone, sulfate conjugate, and glucuronide conjugate. For individual plots actual time will be used. There will be two sets of individual plots: a) separate plots for each meal condition (fasted condition, 1 hour before meal, and 4 hours after meal) and each race (Japanese and Caucasian) with all subjects included and b) with separate plots for each subject with all meal conditions included.

#### *PK Parameters*

The following PK parameters for unchanged edaravone, sulfate conjugate and glucuronide conjugate will be calculated from measured plasma concentrations:  $AUC_{0-t}$ ,  $AUC_{0-24}$ ,  $AUC_{0-\infty}$ ,  $C_{max}$ ,  $t_{max}$ ,  $t_{1/2}$ ,  $Kel$ ,  $MRT^*$ ,  $CL/F^*$ ,  $V_z/F^*$ ,  $V_{ss}/F^*$  (\* only for unchanged edaravone)

The PK parameters will be listed. Summary statistics (N, n, mean, SD, median, minimum, maximum, geometric mean and geometric CV%) will be presented for all PK parameters by treatment (edaravone in fasted condition, or before or after meal) and race (Japanese or Caucasian).

These parameters will also be listed. For all PK profiles for which the  $Kel$  has been calculated, the following will be listed:

- Number of data points used in the regression analysis for estimation of  $Kel$ .
- The lower and upper limits of the time period spanned by the data points used in the regression analysis for estimation of  $Kel$ .
- Adjusted R-squared value.
- Percentage of  $AUC_{0-\infty}$  extrapolated.

For  $C_{max}$ ,  $AUC_{0-t}$ ,  $AUC_{0-24}$  and  $AUC_{0-\infty}$  spaghetti plots or scatter plots will be produced showing individual differences between fasted condition and administration before or after meal, and showing differences in parameter distributions of Japanese and Caucasian subjects.

For  $C_{max}$ ,  $AUC_{0-t}$ ,  $AUC_{0-24}$  and  $AUC_{0-\infty}$  ratios (administration before or after meal/ fasted condition in Japanese subjects) will be calculated for each subject. These will be listed and summary statistics (N, n, mean, SD, median, minimum, maximum) for these will also be presented.

#### **7.9.5 Assessments of effect of meal conditions on pharmacokinetics of Unchanged Edaravone, Sulfate Conjugate, and Glucuronide Conjugate**

PK parameters  $AUC_{0-\infty}$  and  $C_{max}$  of unchanged edaravone, sulfate conjugate, and glucuronide conjugate for each meal condition will be analysed for the assessments of effect on pharmacokinetics of unchanged edaravone, sulfate conjugate, and glucuronide conjugate by meal conditions.

*Descriptive Statistics:*

Pharmacokinetic parameters will be summarized by analyte (i.e. unchanged edaravone, sulfate conjugate, and glucuronide conjugate) in fasted condition, 1 hour before meal, and 4 hours after meal.

*Statistical Analysis:*

A linear mixed effects model will be fitted to log-transformed PK parameters ( $AUC_{0-t}$ ,  $AUC_{0-24}$ ,  $AUC_{0-\infty}$ , and  $C_{max}$ ) including meal condition, period and group as fixed effect and subject as random effect. Meal condition will be in fasted condition, 1 hour before meal or 4 hours after meal. Estimates of mean difference between fasted condition and before or after meals will be obtained with 90% CI for the difference. These estimates and limits will then be back-transformed to obtain ratios of least squares geometric means A 90% CI for the ratio of  $AUC_{0-\infty}$  as well as  $C_{max}$  which lie entirely within the limits of 0.80 to 1.25 provides evidence of no effect of food intake on unchanged edaravone, sulfate conjugate, and glucuronide conjugate.

**7.9.6 Assessments of race on pharmacokinetics of Unchanged Edaravone, Sulfate Conjugate, and Glucuronide Conjugate**

PK parameters  $AUC_{0-\infty}$  and  $C_{max}$  of unchanged edaravone, sulfate conjugate, and glucuronide conjugate in each race will be analysed for the assessments of effect on pharmacokinetics of unchanged edaravone, sulfate conjugate, and glucuronide conjugate by race.

*Descriptive Statistics:*

[figure not shown]
Pharmacokinetic parameters will be summarized by analyte (i.e. unchanged edaravone, sulfate conjugate, and glucuronide conjugate) in Japanese and Caucasian.

*Statistical Analysis:*

A linear model will be fitted to log-transformed PK parameters ( $AUC_{0-t}$ ,  $AUC_{0-24}$ ,  $AUC_{0-\infty}$ , and  $C_{max}$ ) including race as fixed effect. Race will be Japanese or Caucasian. Estimates of mean difference between Japanese and Caucasian will be obtained with 90% CI for the difference. These estimates and limits will then be back-transformed to obtain ratios of least squares geometric means A 90% CI for the ratio of  $AUC_{0-\infty}$  as well as  $C_{max}$  which lie entirely within the limits of 0.80 to 1.25 provides evidence of no effect of race on edaravone, sulfate conjugate, and glucuronide conjugate.

[figure not shown]
● Example Code

SAS code (Cohort1, Group1):

[figure not shown]

SAS code (Cohort1, Group2):

[figure not shown]

SAS code (Cohort2: food effect):

SAS code (Cohort2: racial difference):

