 - Cohort 1: Within 12 weeks before the initiation of victim drug administration
 - Cohort 2: Within 24 hours before visit on Day -1
- (18) Use of any health food(s) containing St John's Wort (*Hypericum perforatum*) within 2 weeks before the initiation of victim drug administration (only in cohort 1)
- (19) Subjects judged by the investigator (or subinvestigator) to be unsuitable for the study for any other reason

Note) Periods are defined as follows:

- One year before informed consent is the same day of the preceding year,
- Twelve (2) weeks before informed consent is the same day of the preceding week 12 (2),
- Seven days before start of dosing is the same day of the preceding week,
- Two weeks before start of dosing is the same day of the preceding week 2.

[Rationales for setting]

- (1) To ensure the safety of subjects and to exclude unhealthy subjects.
- (2) To perform the study safely and ethically.
- (3) To perform the study safely and ethically.
- (4) To reduce PK variability due to BMI differences.
- (5) To perform the study safely and ethically.
- (6) To perform the study safely and ethically.
- (7) With reference to the "Enforcement Regulations for the Act on Securing a Stable Supply of Safe Blood Products," blood collection volumes and intervals are specified to ensure subject safety.

- (8) With reference to the “Enforcement Regulations for the Act on Securing a Stable Supply of Safe Blood Products,” the blood collection interval was specified to ensure subject safety.
- (9) To avoid a possible effect on the PK.
- (10) To assure subject safety, even though there were no toxicity findings at the highest dose of 200 mg/kg in the reproductive and developmental toxicity studies.
- (11) Because this may affect the assessment of this study.
- (12) To perform the study ethically and to avoid any unpredictable effects of drugs whose efficacy and safety have not been established.
- (13) Because this may affect the assessment of PK.
- (14) Because this may affect the assessment of this study.
- (15) Because this may affect the assessment of PK.
- (16) Because this may affect the assessment of PK.
- (17) Because this may affect the assessment of PK.
- (18) Because this may affect the assessment of PK.
- (19) To perform the study safely and ethically.

4. Explanation and Informed Consent

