5.3.2 Methods of Randomization and Allocation

Randomization will be performed only in Cohort 2. The person in charge of subject assignment will create a randomization key code table and provide it for the investigator. After all subjects are given their own subject identification (ID) code, and identification of subjects and standby subjects are completed (inclusion order for standby subjects will

be determined in advance), the investigator (or subinvestigator) will assign the subjects to Group 3, 4, or 5 in ascending numerical order of subject ID code, and give a randomization number to each subject. The randomization numbers will be recorded in the CRF. If a subject is replaced by a standby subject in the final selection of subjects, subject ID codes and inclusion order for standby subjects that have been determined in advance will be parallelized in ascending numerical order after which a replacement will be conducted. The Investigator (or subinvestigator) or study collaborator will submit a copy of the randomization key code table to the sponsor. The investigator (subinvestigator) will start prescription in accordance with each of the dosage planned for each assigned group, i.e. no breakfast after dosing, dosing 4 hours after a meal, or start of a meal 1 hour after dosing. Details of randomization will be specified in documented subject assignment procedures.

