6.1 Sample Size

Total of 84 subjects

Cohort 1: 66 subjects (32 for Group 1, 34 for Group 2)

Cohort 2: 18 subjects (9 Japanese and 9 Caucasian subjects)

[Rationales for setting]

(1) Cohort 1

Because there is no information about pharmacokinetic parameters for coadministration of each victim drug (rosuvastatin, sildenafil, or furosemide) and edaravone, the number of subjects for each group was set as follows based on data about C_{max} and AUC after administration of victim drugs obtained from previous studies and literatures.

- Group 1

Regarding rosuvastatin, based on results of previous studies, geometric CV (intra-individual) of C_{max} and $AUC_{0-\infty}$ was hypothesized to be 21.0% and 23.0%, respectively. On the assumption that when only rosuvastatin is administered and when it is coadministered with edaravone, ratio of both parameters would be 1.00; the number of subjects was calculated to be 20 which would allow power of at least 80% in 2 one-tailed tests with significance level of 5%.

Regarding sildenafil, based on results of previous studies, geometric CV (intra-individual) of C_{max} and $AUC_{0-\infty}$ was hypothesized to be 28.9% and 22.8%, respectively. On the assumption that when only sildenafil is administered and when it is coadministered with edaravone, ratio of both parameters would be 1.00; the number of subjects was calculated to be 29 which would allow power of at least 80% in 2 one-tailed tests with significance level of 5%.

Based on the above results, the target number of subjects was set at 32, which is the total of 3 (an anticipated number of subjects who might withdraw from the study) and 29 (the number of subjects calculated based on sildenafil data).

- Group 2

Based on results of previous studies, intra-individual geometric CV of C_{max} and $AUC_{0-\infty}$ of furosemide was hypothesized to be 29.5% and 11.5%, respectively. On the assumption that when only furosemide is administered and when it is coadministered with edaravone, ratio of both parameters would be 1.00; the number of subjects was calculated to be 31 which would allow power of at least 80% in 2 one-tailed tests with significance level of

5%. Based on the above results, the target number of subjects was set at 34 on the basis that 3 subjects might withdraw from the study.

Based on the above, the target number of subjects was set at 66 for Cohort 1 (32 for Group 1, 34 for Group 2).

(2) Cohort 2

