13.4.1 Analysis of demographic characteristics and other baseline characteristics

Regarding analysis on the following items about demographic characteristics and other baseline characteristics, frequency and percentage will be calculated for the calculated values, and descriptive statistics will be calculated for the numerical data. The calculation will be made for each Cohort and Group.

Assessment item: age, sex, height, body weight, BMI, race, medical history, complications, and concomitant medications

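### The race comparison in SAP 7.9.6 leaves out the randomised group and has no supplementary body-weight analysis or by-race baseline table

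*SAP*

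**What the plan says.** SAP 7.9.6 fits a linear model to log-transformed AUC and Cmax, "including race as fixed effect. Race will be Japanese or Caucasian". It adds that "Estimates of mean difference between Japanese and Caucasian will be obtained with 90% CI for the difference", and that a CI for AUC0-∞ and Cmax "which lie entirely within the limits of 0.80 to 1.25 provides evidence of no effect of race". Protocol 13.4.2 gives no race model, so SAP 7.9.6 is the only specification. The example SAS code does not appear in the text available, so its terms could not be checked.

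The food-effect model in SAP 7.9.5 is fitted "including meal condition, period and group as fixed effect and subject as random effect".

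On design, Protocol 5.2.1.2 shows 3 Japanese and 3 Caucasian subjects receiving the fasted dose in each group, on Day 1 (Group 3), Day 4 (Group 4) or Day 7 (Group 5). Cohort 2 is randomised, and under Protocol 5.3.2 the investigator will "assign the subjects to Group 3, 4, or 5 in ascending numerical order of subject ID code". Protocol 8.3 gives every Cohort 2 subject the same dose, not scaled to weight.

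On body size, Protocol 3.3 limits BMI to 18.0–30.0 and weight to at least 50 kg, with the rationale "To reduce PK variability due to BMI differences". Protocol 9.2.1.5 records weight at screening and admission. For baseline tables, Protocol 13.4.1 says "The calculation will be made for each Cohort and Group". SAP 7.5 summarises weight, BMI, race and smoking status and lists them by subject, but plans no split by race.

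**The concern.** Race is a stated secondary objective of Cohort 2. Protocol 5.2.1.3 reopens it because the earlier oral study found Caucasian Cmax and AUC at 75% and 79% of Japanese values. It is also the only between-subject PK comparison in the plan, so it depends most on how subject differences are handled.

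There are two separate gaps:

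- **Group.** The fasted records come from three randomised blocks, each containing both races and dosed on a different day. The food model uses this structure and the race model does not.
- **Body weight.** At a common fixed dose, a weight difference between the races could contribute to the observed ratio. The plan collects weight but has no analysis or by-race table showing whether the races differed in size. Each Cohort 2 group mixes the races, so a table by cohort and group does not show it either.

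If the trial again finds a ratio near 0.75–0.79, the planned outputs cannot say whether it tracks body size.

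A smaller point is that SAP 7.9.6 does not say the model uses fasted records only. Caucasians are dosed fasted only, while Japanese subjects have three meal conditions. The model has no meal or subject term, so the restriction should be explicit.

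**Working it through.** **No stated figure to reproduce.** Protocol 6.1 says the Cohort 2 size has no statistical calculation behind it. As a check on the two one-sided tests (TOST) formula used in step 5, the same formula applied to Cohort 1 gives n = 20 for rosuvastatin AUC (CV 23.0%, stated 20) and n = 31 for furosemide Cmax (CV 29.5%, stated 31). For sildenafil Cmax (CV 28.9%) it gives power 0.800 at the stated 29.

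**1. Group and bias.** With 3 + 3 in each group, race and group are orthogonal. The variance factor of the race difference is 2/9 = 0.2222 with or without group. In a simulated data set with large group effects the race estimate was −0.23567 both ways. Omission therefore causes no bias in the planned layout.

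**2. Group and precision.** Residual df are 18 − 2 = 16 (race only) and 18 − 4 = 14 (race + group). The 95th t percentiles are 1.746 and 1.761.

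- No group effect: 1.761/1.746 = 1.009, so the log-scale half-width is 0.9% wider. The back-transformed CI factor moves from 1.177 to 1.179 at CV 20% and from 1.373 to 1.377 at CV 40%.
- Break-even: group must remove 1 − (1.7459/1.7613)² = 1.7% of residual variance.
- With between-day log SD g and residual log SD s (both assumed), half-width ratio = 1.761 s / {1.746 √[(14s² + 2(s² + 6g²))/16]}.

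| g | s = 0.20 | s = 0.35 |
|---|---|---|
| 0 | 1.009 | 1.009 |
| 0.10 | 0.926 | 0.979 |
| 0.15 | 0.846 | 0.946 |

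**3. Group if balance breaks.** Suppose one Japanese subject in Group 5 is lost before the Day 7 fasted dose, and Day 7 values are offset by δ on the log scale. The Group 5 share is then 2/8 for Japanese and 3/9 for Caucasians. A race-only model shifts by δ × (1/3 − 1/4) = δ/12. For assumed δ of 0.10 to 0.30 that is 0.008 to 0.025, or about 0.8% to 2.5%. If the day effects are additive, a group term removes it.

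**4. Weight.** The documents give neither weights by race nor an exposure–weight relation. Assume a Caucasian/Japanese weight ratio r of 1.0 to 1.3 and exposure proportional to weight^(−b), with b from 0 to 1. The ratio due to weight alone is r^(−b):

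| r | b = 0 | b = 0.75 | b = 1 |
|---|---|---|---|
| 1.0 | 1.00 | 1.00 | 1.00 |
| 1.1 | 1.00 | 0.93 | 0.91 |
| 1.2 | 1.00 | 0.87 | 0.83 |
| 1.3 | 1.00 | 0.82 | 0.77 |

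The shift is 0% to 23%. To explain an AUC ratio of 0.79 entirely, r would have to be (1/0.79)^(1/b): 1.27 for b = 1, or 1.37 for b = 0.75.

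Adjusting for weight inflates the variance of the race term by about 1 + d²/4, where d is the race gap in within-race SDs of weight: 1.25 at d = 1 and 2.0 at d = 2. Residual df fall to 13.

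**5. Chance of meeting 0.80–1.25.** For 9 v 9, true ratio 1.00 and SE = s√(2/9), TOST power at assumed CVs of 20%, 30% and 40% is 48%, 6% and 0.4% with race only. With group added and no variance removed it is 47%, 6% and 0.6%.

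**The case against.** The strongest reply is that the unadjusted ratio at a common dose is what the objective asks for. If body size is part of how the races differ, adjusting for it answers a different question, and does so imprecisely with 18 subjects. That stands, and it is why the weight model should be supplementary.

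Second, the only statement in the documents on weight and edaravone PK points the other way. The intravenous population PK analysis (Protocol section 1, clinical results) found no notable difference by body weight. This counts, and it is why the range in the working includes an exponent of 0. But the same sentence also reports no difference by race, and the sponsor still reopened race for oral dosing. It does not settle weight for oral dosing either.

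Third, a reader might infer that leaving out group lets body size pass as a race effect. The documents do not support that: group is balanced over race, so its omission touches precision only, or balance after losses. A reader might also take the BMI rationale to mean that body size drives edaravone exposure. It is a general reason for an entry limit, it concerns BMI, and the limits already narrow the range.

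Fourth, the contrast with SAP 7.9.5 is limited. That is a three-period crossover model, where such terms are standard. On fasted data each subject has one record, and group and dosing day are the same factor. Nor is group an identical block for both races: at the fasted dose, Japanese subjects in Groups 4 and 5 have had one or two earlier doses and Caucasians none. Carryover should be small. At the longest half-life given (11.8 h), the 69 h from an 11:00 dose to an 08:00 dose three days later leaves 0.5^(69/11.8), about 1.7%.

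Finally, SAP 7.5 lists individual demographics, so weight by race could be assembled by hand. The missing table is a gap in presentation.

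**Conclusion.** The point holds in a limited form and is worth correcting.

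- The model has race as its only term and ignores a randomised block containing both races. In the planned 3 + 3 layout this costs precision only: from 0.9% in favour of omission (no day effect) to a CI that group would narrow by 2–15% (between-day log SD 0.10–0.15, assumed). Unequal losses after dosing could add a small bias. Reserves under Protocol 8.2 replace only subjects excluded before dosing.
- Any weight difference between the races is contained in the unadjusted ratio, and nothing planned would show it. The possible shift is 0% to 23% on assumptions the documents neither supply nor exclude.

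It would be tempting to conclude that body size explains the earlier 0.79. The documents do not support that. They give no weights by race, and a full explanation needs a weight ratio of 1.27 or more with a steep exponent. Nor is the unadjusted ratio wrong: it is a valid estimate of the total difference between the races and should stay the main result. Neither term makes the no-effect rule attainable with 9 v 9 unless it removes much of the residual variance.

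**What to change.** In SAP 7.9.6:

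1. State that the race analysis uses fasted records only, one per subject.
2. Fit race + group (three levels) to log AUC and Cmax, and keep this weight-unadjusted ratio with its 90% CI as the main result.
3. Add a supplementary model with race + group + ln(admission body weight), reported with its 90% CI and labelled exploratory.

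In SAP 7.5, tabulate Cohort 2 age, weight, BMI and smoking status by race. Smoking belongs there because Protocol 3.3 restricts nicotine for only 24 hours before the visit in Cohort 2, against 12 weeks in Cohort 1, and gives PK assessment as the reason for the criterion.

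The cost is one extra model and one table split, using data already collected. Group uses 2 df. The weight-adjusted CI will probably be wider: √1.25 = 1.12 to √2.0 = 1.41 times if the races differ by 1 to 2 SD in weight, before any fall in residual variance and apart from the loss of one further df.
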